#### 10. Describe the means of analyzing the data and evaluating the results.

- *State the anticipated methods to be used for analysis and interpretation of the data.*
- *The methods must compliment the design of the study and the nature of the data which is being collected.*

Primary outcome measures for testing hypotheses will be walking speed measured during 10m walk trials and foot-to-floor clearance as measured by vertical displacement of marker placed over the first metatarsal using our 16-camera VICON motion analysis system. Force sensing resistors (FSRs) will be used to detect any toe dragging as a result of insufficient foot clearance. Secondary measures will be peak hip, knee and ankle flexion during swing, hip-knee coordination changes, knee flexion during stance and in pre-swing, step length symmetry and 6min walking distance.

The within subject experimental design will be used because it requires fewer subjects with more statistical power while reducing the potential for systemic error or selection bias to test the effect of CV on walking. While practice and carryover effects are major disadvantages of this study design, proper precautions including rest periods between tests and randomization of testing order for treatment group will be instituted to minimize them†. In addition to comparison between treatment and control groups, subjects receiving CV can also serve as their own controls by first comparing volitional gait at baseline (VGB) with any gait correction with the CV approximating desired normal muscle activity (CVN). Next the volitional gait *post*- 12 sessions of training with vibration (VGP) will be compared to volitional gait at baseline (VGB). Thus, any improvements at baseline with CVN compared to volitional gait (VGB) can be attributed to short term effects of vibration. Improvements in volitional gait *post* training with vibration (VGP) compared to baseline gait (VGB) will be attributed to long term effects of vibration. The control group subjects will be evaluated at baseline (VGB) and after gait training (VGP) and compared to the intervention group to identify trends and further explore the potential effects of CV. While this study design has limited generalizability due to the inhomogeneity of the selected population, it can be quite useful for developing and refining CV intervention.

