A one-way repeated measures ANOVA will be used to test for significant difference between means to test Hypotheses 1 and 2. The Tukey honestly significant difference multiple comparison test will be used between each pair of mean walking speeds, foot-to-floor clearance and maximum joint angles to determine 95% ( $p < 0.05$ ) confidence intervals for

statistically significant differences between conditions (CVN-VGB, CVN-VGP, VGP-VGB) and between groups to identify trends across all subjects.

† Greenwald AG. With-in subject design: to use or not to use? *Psychological Bulletin*, 83(2):314-320, 1976.

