**11. Provide a BRIEF DESCRIPTION of how the estimated number of study subjects needed for this research was determined**

- *If this is a quantitative study provide the method of determining sample size estimates.*
- *If multiple studies are planned provide a power analysis or justification for each one.*

A statistical power of 90% was used to determine the number of trials with VICON motion analysis system required for the testing and comparison of temporal and spatial gait parameters. The results indicated a requirement of 30 strides of data or roughly 6 trials (approximately 5 strides per trial) for each condition (volitional or CV). Because this is a two year feasibility study to determine the effect size a small sample of 6 subjects were chosen for intervention with six controls to obtain preliminary data for calculating statistical power for the number of subjects required in a larger study to determine the effect of vibration on improving gait in MS.

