**Recruitment and baseline evaluation**

Potential subjects will be identified via chart review or through referral and asked if they would be willing to participate in the study. If agreeing, they would undergo the consent process. Twelve subjects with gait disorders from MS will be recruited for participation in this study, with six subjects assigned to undergo CV gait training and six to control group for gait training without vibration. Subjects will be randomly assigned to either treatment or control group and matched by functional walking category based on speed for data analysis†. After signing the consent form agreeing to participate in the study and meeting inclusion/exclusion criteria, subjects will undergo baseline evaluation. This will include walking speed and distance and using VICON system for temporal and spatial parameters, kinematics and kinetics of gait and EMG activity during volitional gait at their preferred walking speed.

Retro-reflective markers will be placed on the bony landmarks and surface EMG electrodes over target muscles while the subject walks along the 10m walkway instrumented with force platforms. Standard analysis software provided with VICON system will be used to track markers in 3D and calculate all gait parameters so they can be correlated with muscle activity. The baseline evaluation will be done with and without vibration on treatment group and without vibration on control group. Data will be collected during 6 walking trials of at least 5 steps per trial (approximately 30 steps) within the visual field of the VICON motion analysis system under each condition. Sufficient resting time will be provided between trials to complete the assessment. Subjects will be encouraged to use their walking aid while a trained physical therapist provides standby guard during walking for their safety.

[figure not shown]

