### Gait training

Each group will undergo twelve 2 hour sessions of standard gait training (up to 3x/week based on availability). Both groups will receive the same gait training while the treatment group will receive gait training with CV and control group without it.

Up to four vibrators per leg powered by the vibration stimulation control unit (VSCU) will be strapped or taped over ankle dorsiflexor tibialis anterior (TA), knee extensor and hip flexor rectus femoris (RF), knee flexor short head of biceps femoris (BF) and hip flexor and abductor the lateral portion of tensor fasciae latae muscles (TFL) as shown in figure. The cylindrical vibrators will be used to increase vibration intensity as needed. The CV paradigm resembling normal activity of muscles timed to gait events, as detected by accelerometers taped to the shoes and force sensing resistors placed in the insoles, will be imposed during walking. An average frequency of vibration will be set at 80Hz and as high as 150Hz. Physical therapist will conduct all gait training and encourage maximal voluntary effort during training while providing standby assist and spotting the subjects to ensure safety. During walking, heart rate (HR) will be monitored with the chest strap monitor and receiver watch and recorded before and after each walk. Blood pressure (BP) will be measured before and after each session of CV training and evaluation. In addition, subjects will be asked during each session if they experience any untoward sensation. BP and HR during gait training with vibration will be monitored and compared to baseline values. An increase in BP and HR of >20% and experiencing untoward sensation will be considered significant to reject Hypothesis that CV produces no physiological changes.

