Statistical Analysis Plan

Study Title: Cyclical muscle vibration in multiple sclerosis to improve walking

Last update: 01/29/2020

The within subject experimental design was used for this feasibility study because it requires fewer subjects with more statistical power while reducing the potential for systemic error or selection bias to test the effect of training with vibration on walking. While practice and carryover effects are major disadvantages of this study design, proper precautions including rest periods between tests and randomization of testing order for walking with or without vibration was instituted to minimize them at baseline and post-treatment¹. In this study design, any improvements at baseline with vibration compared to volitional gait can be attributed to short term effects of vibration. Improvements in volitional gait *post* training with vibration compared to volitional baseline gait can be attributed to long term effects of vibration. While this feasibility study design has limited generalizability due to the small number of subjects and inhomogeneity of the selected population, it can be quite useful for developing and refining future vibration intervention studies.

Means and standard deviations were calculated for all outcome measures for each subject. Differences in means were determined via a two-way analysis of variance ($p < 0.05$). A statistical power of 90% was used to determine the number of trials with VICON motion analysis system required for the testing and comparison of gait parameters. The results indicated a requirement of 30 strides of data or roughly 6 trials (approximately 5 strides per trial) for each condition (volitional or with vibration).

¹ Greenwald AG. With-in subject design: to use or not to use? *Psychological Bulletin*, 83(2):314-320, 1976.

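### The vibration arm's own before-after change is credited to vibration, although that arm also has the same 12 gait-training sessions as controls

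*SAP*

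**What the plan says.** **Treatment received.** Protocol item 13 (Gait training) gives each arm twelve 2-hour sessions: "Both groups will receive the same gait training while the treatment group will receive gait training with CV and control group without it". Item 14 assigns the arms at random; item 11 plans six subjects in each.

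**Attribution rule.** Protocol item 10 says that improvement in volitional gait after training "compared to baseline gait (VGB) will be attributed to long term effects of vibration". The SAP's first paragraph repeats the rule: improvement after "training with vibration compared to volitional baseline gait can be attributed to long term effects of vibration".

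**Between-arm comparison.** It exists in the protocol. Item 10 introduces the within-subject contrasts with the words "In addition to comparison between treatment and control groups, subjects receiving CV can also serve as their own controls", and has controls assessed at VGB and VGP. It extends the Tukey comparisons to conditions "and between groups to identify trends across all subjects". The test named for the hypotheses is different: "A one-way repeated measures ANOVA will be used to test for significant difference between means to test Hypotheses 1 and 2".

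**SAP model.** The SAP specifies a two-way analysis of variance without naming its factors. It mentions neither a control arm nor group assignment.

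**Use of the results.** Item 11 says the subjects were chosen "to obtain preliminary data for calculating statistical power for the number of subjects required in a larger study".

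**The concern.** Hypothesis 2 (Protocol item 9) is that vibration leaves a lasting improvement in walking. The contrast tied to it, VGP minus VGB in the vibration arm, also contains 12 × 2 = 24 hours of gait training and a second round of testing. One arm alone cannot separate these.

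Both documents concede that practice effects are a weakness and offer rest periods and randomised test order as precautions. Those act within an evaluation visit. They do nothing about training that takes place between the two visits. The control arm could separate training from vibration, but neither document makes that comparison the basis for the conclusion.

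Two things are at stake. A benefit of training could be reported as a lasting effect of vibration. And if the effect size for the larger study came from the within-arm change, it would include the training effect and make that study too small.

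**Working it through.** **The plan's own figure.** The only power-based number is 30 strides per condition (6 trials × about 5 strides = 30) at 90% power. It concerns strides, not subjects, and gives no effect size or SD, so its power cannot be reproduced. It does not bear on this point.

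**Step 1: what each contrast contains.** Let T be the effect of training, P of retesting and V of adding vibration.
- Vibration arm, VGP − VGB: T + P + V
- Control arm, VGP − VGB: T + P
- Difference between arms: V

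The within-arm contrast equals V only if T + P = 0. The baseline contrast of walking with and without vibration (CVN − VGB) precedes training and is not affected.

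**Step 2: false attribution when V = 0.** Inputs from the documents: n = 6 per arm, p < 0.05 (two-sided assumed), three conditions in the Tukey set. Assumed: T + P shifts the change by d SDs of change. The noncentrality is √6 × d.
- Paired t-test: df 5, critical t 2.571.
- Protocol's Tukey comparison: error df (3−1)(6−1) = 10, sphericity assumed, critical t = 3.877/√2 = 2.741.

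| d (assumed) | noncentrality | Tukey | paired t | between arms |
|---|---|---|---|---|
| 0.5 | 1.22 | 11% | 17% | 5% |
| 0.8 | 1.96 | 27% | 36% | 5% |
| 1.0 | 2.45 | 43% | 51% | 5% |
| 1.5 | 3.67 | 80% | 83% | 5% |

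The between-arm column holds for every d because an equal shift cancels; simulation gave 4.9% to 5.2% for the two-sample t-test on change.

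**Step 3: planning the larger study.** Assume V = 0.5 SD of change, and that the within-arm change is used as the effect size. Two-sample t-test, two-sided 0.05, 80% power:

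| T (assumed) | within-arm effect | n per arm planned | true power at 0.5 SD |
|---|---|---|---|
| 0.25 | 0.75 | 29 | 46% |
| 0.5 | 1.0 | 17 | 29% |
| 0.8 | 1.3 | 11 | 20% |

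The number needed at 0.5 SD is 64 per arm.

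**Step 4: precision of the between-arm estimate, 6 per arm.**
- Change score: 95% CI half-width = t(0.975; 10) × √(2/6) = 2.228 × 0.577 = 1.29 SD of change. Power for a true 1 SD effect is 35%.
- ANCOVA on VGB: half-width = t(0.975; 9) × √(2/6 + baseline imbalance term) × √((1+r)/2), where r is the VGB–VGP correlation and the variance is assumed equal at both visits. Averaged over chance imbalance this is 1.20 (r = 0.5), 1.31 (r = 0.8) and 1.36 (r = 0.95). The documents give no r.

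**The case against.** The strongest reply is that the protocol already plans the right comparison. Item 10 lists it ahead of the within-subject contrasts, and the SAP's two-way ANOVA may be group by time, in which case its interaction is the contrast wanted. That reading is possible. But the SAP discusses only vibration on or off and baseline or post-training, so condition by time fits at least as well. Under either reading the attribution sentence still directs the wrong inference. The Step 2 percentages describe the within-arm contrast, tested by the protocol's Tukey procedure or by a paired t-test that neither document names; they do not describe a group-by-time interaction.

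Three further points stand as limits:
- No passage says the larger study will take its effect size from VGP − VGB; item 11 names the controls among the subjects who supply the data. Step 3 is therefore conditional.
- The between-arm estimate is noisy. With a true effect of 0.5 SD and 6 per arm, the observed standardised difference is at least 1.0 in about 22% of trials and zero or negative in about 19%. The point estimate alone should not size a trial.
- Controls train without vibrators and no sham is described, so the arm difference may also include expectation and encouragement.

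That this is a small feasibility study limits what any test can show. It does not justify crediting a mixed change to one of its components.

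**Conclusion.** The concern holds. The long-term attribution is wrong as written in both documents, and it is the only rule the SAP gives for the long-term conclusion. Under assumed training shifts of 0.5 to 1.5 SD of change and no vibration effect, following it gives a significant result credited to vibration in 11% to 80% of trials (Tukey) or 17% to 83% (paired t), against 5% for the randomised comparison. The confounding itself needs no assumption beyond both arms receiving the same training; its size depends on a training effect that the documents do not give. The protocol's planned group comparison narrows the problem without removing it, because that comparison is not what Hypothesis 2 is judged on.

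**What to change.** 1. Base Hypothesis 2 on the between-arm comparison for both primary outcomes (walking speed and foot-to-floor clearance), with one mean per subject per visit, reported as an estimate with a 95% CI.
2. Name one estimator in advance: ANCOVA of VGP on group and VGB, or the difference in change (group by time). Either cures the attribution; the choice must not follow the results.
3. Name the factors of the SAP's two-way ANOVA.
4. Item 13 has subjects "matched by functional walking category based on speed for data analysis". State how that matching enters the model, or that it does not.
5. Replace the attribution sentences in Protocol item 10 and the SAP with wording such as: *Change within the vibration arm reflects gait training, repeated testing and vibration together; only the difference from control is used to estimate the effect of adding vibration.* Note that no sham is described. Keep the within-arm contrast as descriptive.
6. Take planning values for the larger study from the between-arm estimate and its interval, not from the point estimate alone.

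**Cost.** No new data are needed, because control assessments at VGB and VGP are already planned. The price is precision: a half-width of about 1.29 SD of change and 35% power at 1 SD, so the result will be an estimate rather than a firm test. The SAP is written in the past tense; if the data have been analysed, the change of main contrast must be disclosed as post hoc.

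### The SAP swaps the protocol's repeated measures ANOVA for a two-way ANOVA with no stated factors, error term or unit of analysis, so its p-values cannot be tied to patients

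*SAP*

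**What the plan says.** The SAP is a single page. It calls the design within-subject and justifies it by needing fewer subjects for more power. It credits baseline differences with vibration to short-term effects, and the change in volitional gait from baseline to after training to long-term effects of vibration. Its statistical content is "Means and standard deviations were calculated for all outcome measures for each subject. Differences in means were determined via a two-way analysis of variance" at p < 0.05.

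The only power statement is "A statistical power of 90% was used to determine the number of trials with VICON motion analysis system required", which gives "The results indicated a requirement of 30 strides of data or roughly 6 trials (approximately 5 strides per trial) for each condition". No power is stated for subjects.

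Protocol item 10 planned a one-way repeated measures ANOVA with Tukey comparisons among three conditions (volitional baseline, vibration at baseline, volitional post-training) and between groups. Protocol item 11 says six treated and six control subjects were chosen "to obtain preliminary data for calculating statistical power for the number of subjects required in a larger study".

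**The concern.** A two-way ANOVA can mean several things here: vibration by session, group by time, or subject by condition. Its observations could be strides, trials or subject means. The SAP settles none of this, and the term that would have settled the error structure (repeated measures) has gone.

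The choice matters because all baseline strides of a subject come from one evaluation and all post-training strides from another. If stride-to-stride noise is the error, any ordinary day difference in speed or foot clearance can look significant, and the SAP would attribute it to vibration training. If subject means are analysed without a subject term, the large differences between people go into the error, and the advantage the SAP claims for its design is lost.

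The study's product is also at stake. Sizing a larger study needs the between-subject SD of change. The SAP plans SDs for each subject, which describe variation between strides or trials and cannot replace it.

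**Working it through.** **The plan's own figure.** 6 trials x 5 strides = 30, as stated. The 90% power cannot be reproduced, because no effect size, SD or test is given. Solving backwards at two-sided 0.05, (1.960 + 1.282) x sqrt(2/30) = 0.84 stride SD for independent strides, or 3.242/sqrt(30) = 0.59 if paired. Either is an effect measured against stride noise, not against variation between patients.

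**Inputs.** From the documents: 6 treated and 6 control subjects, 30 strides per condition, alpha 0.05. Assumed, because the documents give no variance components: stride SD = 1; tau = SD of a subject's session mean, in stride SDs; the between-subject variance; the correlation between conditions.

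**A. Strides as error, post-training versus baseline, no true effect.** The true variance of the difference exceeds the assumed one by the ratio (tau² + 1/30)/(1/30) = 1 + 30 tau². Type I error is 2 x [1 - Phi(1.96/sqrt(ratio))].

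| tau | ratio | 1.96/sqrt(ratio) | one subject | pooled, no subject term, between-subject variance 1 | same, variance 5 |
|---|---|---|---|---|---|
| 0.1 | 1.3 | 1.72 | 8.6% | 3% | 0.3% |
| 0.25 | 2.875 | 1.16 | 24.8% | 12% | 3% |
| 0.5 | 8.5 | 0.67 | 50.1% | 33% | 16% |
| 1.0 | 31 | 0.35 | 72.5% | 58% | 41% |

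The last two columns are simulations of six subjects. Pooling six subjects with subject as a fixed factor gives rates close to the one-subject column: about 9%, 24%, 50% and 72% with the subject-by-session interaction fitted, and 9%, 24%, 48% and 67% without it. So the inflation comes from using strides as error. A fixed subject factor does not cure it, and leaving subject out can mask it.

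**B. With versus without vibration in the same evaluation, strides as error.** Session variation cancels. With no subject term, simulated type I error is 0.1% to 1.2%; with subject fixed it is about 5%. It rises to 13% to 29% (no subject term) or about 45% (subject fixed) only if subjects also differ in their response to vibration (assumed variance 0.1).

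**C. Group by time on strides, 6 versus 6, no subject term.** Interaction type I error is 10% to 34% for session variances of 0.05 to 0.25, against about 5% for a t test on subject change scores.

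**D. Subject means in an ordinary 2x2 ANOVA (vibration by session, 6 subjects).** At correlation 0.8, type I error is about 0.1%. For an effect of one SD of the paired difference, power is:

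| correlation | ordinary ANOVA | within-subject test |
|---|---|---|
| 0.9 | 8% | 79% |
| 0.8 | 26% | 79% |
| 0.5 | 69% | 79% |
| 0.3 | 82% | 79% |

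The 79% belongs to a main effect that averages two differences per subject, so the effective effect is 1 x sqrt(2) = 1.41 SD (noncentrality 1.41 x sqrt(6) = 3.46, 5 df). A single paired contrast has noncentrality 1 x sqrt(6) = 2.45 on 5 df and power of about 51%.

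**E. Subject as the error stratum.** Simulated type I error is 4.3% to 5.7% in every scenario.

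**The case against.** A reader might infer that the SAP has no subject term and tests strides. The documents do not establish that. Subject could be one of the two factors, the two-way model could have been run as repeated measures in keeping with the within-subject label, or the per-subject means could be the data. The 30 strides are stated as a collection target, which can be read as a question of measurement precision. This objection stands, so the point is an unspecified analysis whose plausible readings include faulty ones. It does not remove the problem: subject as a fixed factor with strides as error still inflates the training contrast.

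A reader might also infer that session variation produces false short-term effects. It does not. That contrast is taken within one evaluation, and the SAP says testing order was randomised. Inflation there needs subjects to differ in their response.

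It is equally tempting to say that pooling always inflates. With no subject term and large differences between people, which the SAP's remark on an inhomogeneous population makes plausible, the pooled test can fall below 5% when session variation is small.

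Finally, this is a feasibility study, and every rate above rests on assumed variances. That tempers the weight of any single p-value. But the SAP sets a p < 0.05 threshold and attributes changes to vibration, and this is its only test.

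**Conclusion.** The concern holds in conditional form. The SAP departs from the protocol's repeated measures model without explanation and leaves factors, error term and unit open, while its only power reasoning counts strides.

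With strides or trials as error, the training contrast has type I error of about 9% to 72% over the assumed tau range of 0.1 to 1.0, for one subject or with a fixed subject term. Without a subject term the result ranges from conservative to strongly inflated, depending on between-subject variance. With subject means in an ordinary two-way ANOVA the test is conservative: the power loss is severe at correlations of 0.8 to 0.9, about 10 points at 0.5, and absent at 0.3. The sizes depend on those assumptions. What does not depend on them is that p < 0.05 cannot be read as a statement about patients until the unit and error term are given.

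**What to change.** Replace the SAP's ANOVA sentence with text to this effect:

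*The trials of each condition and visit are averaged to one value per subject. All tests use these values with subject as the random unit: repeated measures or paired differences in the treated arm, and subject-level change scores between arms. Strides and trials are not replicates; their per-subject SDs are descriptive. The between-subject SD of change is reported for each primary outcome and used to plan the larger study.*

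The SAP should also name the factors and explain the change from Protocol item 10. If a subject-level repeated measures analysis was in fact run, a sentence saying so settles the test, and only the SD of change needs adding.

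The cost is wording and a re-run on the same data. Intervals will be wider and fewer results significant than with a stride-level test: a single paired contrast in six subjects has about 51% power for a 1-SD change.

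The change repairs the error term only. A pre-post test within the treated arm still cannot separate gait training or practice from vibration. Under Protocol item 13 the controls receive the same training without vibration, so a claim of a long-term vibration effect must rest on the between-arm comparison.

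### The treated arm's change after training is credited to vibration although both arms get the same training, and neither document specifies the between-arm model that would separate the two

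*SAP*

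**What the plan says.** **Model.** Protocol item 10 states: "A one-way repeated measures ANOVA will be used to test for significant difference between means to test Hypotheses 1 and 2". It adds Tukey comparisons to find "statistically significant differences between conditions (CVN-VGB, CVN-VGP, VGP-VGB) and between groups to identify trends across all subjects". VGB and VGP are volitional gait at baseline and after training; CVN is walking with cyclical vibration patterned on normal muscle activity. The SAP (last update 01/29/2020, past tense) states only "Differences in means were determined via a two-way analysis of variance", at p < 0.05.

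**Attribution.** In item 10, volitional gains after training "compared to baseline gait (VGB) will be attributed to long term effects of vibration". The SAP keeps the rule: gains in volitional gait after "training with vibration compared to volitional baseline gait can be attributed to long term effects of vibration".

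**Controls.** Item 10 says "The control group subjects will be evaluated at baseline (VGB) and after gait training (VGP) and compared to the intervention group to identify trends", and continues that this will also help explore what vibration may do. Item 13 (Gait training) says "Both groups will receive the same gait training while the treatment group will receive gait training with CV and control group without it". Item 13 (Recruitment and baseline evaluation) randomises six subjects to each arm, matches them by walking-speed category for analysis, and says "The baseline evaluation will be done with and without vibration on treatment group and without vibration on control group". The SAP does not mention a control group.

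**The concern.** Twelve two-hour sessions of gait training with a physical therapist may improve walking by themselves. If so, VGP minus VGB in the treated arm is positive even when vibration adds nothing, and the rule in both documents reports that gain as an effect of vibration. Rest periods and randomised test order deal with order effects within a visit; they do not remove a gain between visits.

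The study recruited a randomised control arm that can separate the two, but neither document gives a model that uses it. Item 11 says the aim is an effect size for planning a larger study. An effect size that contains the training gain would make that study too small. In addition, a reader of the SAP cannot tell which comparison its p < 0.05 refers to.

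**Working it through.** **The plan's own figure.** The only powered quantity is 30 strides per condition (6 trials × about 5 strides = 30). Its 90% power cannot be reproduced because no effect size or SD is given, and the point does not depend on it.

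**1. What each comparison estimates.** Let g be the mean gain from the shared training and v the mean extra gain from training with vibration.
- Treated arm, VGP − VGB: g + v
- Control arm, VGP − VGB: g
- Difference between arms: (g + v) − g = v

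Both documents attribute the first line to vibration. Only the third line is vibration.

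**2. What each named model can test.**

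| Model | Where | Can it estimate v? |
|---|---|---|
| One-way repeated-measures ANOVA with Tukey | Protocol item 10 | No. It has no group term, and comparing group means is not comparing changes |
| Two-way ANOVA read as group × visit | SAP, not stated | Yes |
| Two-way ANOVA read as vibration × visit, treated arm | SAP, not stated | No. It has no controls |

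One two-way model cannot be both of the last two, because controls are never assessed with vibration.

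**3. Size of the attribution problem (illustration).** From the documents: 6 per arm and a 5% level, taken as two-sided. Assumed: v = 0, no short-term vibration effect, g = 0.5, 1.0 or 1.5 in units of the between-subject SD of change, and equal SDs for all pairwise differences.

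- *Unadjusted paired t, treated arm:* noncentrality g√6 = 1.22, 2.45, 3.67 on 5 df, critical value 2.571. Significant in 17, 51 and 83%.
- *Tukey VGP − VGB after the protocol's ANOVA (three conditions, 10 error df):* declare significance if |difference in means| / √(MSE/6) exceeds 3.877. By simulation, significant in 11, 43 and 80%, and in 2% when g = 0.
- *Between-arm test of change:* g cancels, so the test stays at 5% for every g.

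**4. What the between-arm test can deliver with 6 + 6.**
- Without matching, 10 df: 95% CI half-width = 2.228 × √(2/6) = 1.29 SD.
- Noncentrality is v/√(2/6) = 1.732v. Power is 12, 35 and 65% at v = 0.5, 1.0 and 1.5 SD; 80% power needs v = 1.80 SD.
- If the matching means six pairs, there are 5 df and the half-width is 2.571 × √(2(1 − ρ)/6). For an assumed within-pair correlation ρ of 0, 0.3 or 0.5 this is 1.48, 1.24 or 1.05 SD, with power at 1 SD of 29, 39 or 51%.

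**The case against.** **A between-arm comparison is planned.** This stands. Item 10 refers to comparing treatment with control, to comparing controls with the intervention group on VGB and VGP, and to Tukey comparisons between groups. A reader might infer that controls are ignored or serve only to show trends; the protocol's wording is wider than that. What is missing is a model for the comparison, and the attribution rule does not wait for its result.

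**The SAP's two-way ANOVA may be valid.** This also stands. Group × visit is a possible reading, and the SAP may be a deliberate update. The gap is that it names no factors. Its prose describes only vibrated against volitional gait and post-training against baseline.

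**Further faults might be inferred, but the documents do not establish them.**
- *Strides treated as independent.* The SAP computes means for each subject and nowhere says that strides were pooled.
- *Multiplicity control abandoned.* The SAP is silent on Tukey, which does not show that it was dropped.
- *Post-training vibration data left out of the contrasts.* That holds only if CVN means baseline. Item 10 can also be read as naming a condition at either visit, so this is an ambiguity.

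**It is a feasibility study.** Item 11 claims no subject-level power, and with 6 per arm the between-arm test is weak. That is a reason to report an estimate with its interval. It does not justify crediting a within-arm change to vibration.

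**Conclusion.** The attribution is wrong as written in both documents. The treated arm's VGP − VGB change is training plus vibration, and it is assigned to vibration alone. This follows from the design and needs no assumed numbers. How often it would mislead depends on the size of any training gain, which the documents do not give; the 11, 43 and 80% figures (17, 51 and 83% unadjusted) are conditional on assumed shared gains of 0.5, 1.0 and 1.5 SD.

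The protocol's one-way repeated-measures ANOVA and the SAP's two-way ANOVA are also unreconciled. The first cannot supply the planned group comparison; the second is too thinly described to tell whether it does.

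The short-term contrast at baseline (CVN − VGB) is not affected, because it is made before training within the same subjects. The point should be fixed, but it does not show that the analysis already run was invalid.

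**What to change.** 1. **Reword the attribution sentence** in protocol item 10 and the SAP. A long-term effect of vibration is inferred only from the between-arm difference in VGP − VGB change. Analyse one mean per subject per visit, group × visit with subject as a random effect, and report the estimate with a 95% CI. State whether the matching by walking category in item 13 enters the model, because it changes the degrees of freedom and the precision.
2. **Add a dated SAP clarification** that names the factors, error term and multiplicity method of the two-way ANOVA actually run, and reconciles it with the protocol's one-way model and Tukey test. The SAP's past tense suggests the analysis has been done, so a between-arm analysis added now should be labelled post hoc.
3. **Define CVN** as baseline only or both visits, and state the role of the post-training vibration data.

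Cost: wording, and at most a re-analysis of existing data. The downside is that fewer results may reach p < 0.05 and the between-arm interval will be wide, about ±1.3 SD without matching.
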